9.2 Pre-Screening prior to HIPAA Authorization

Will any of the identification methods checked above involve access to Protected Health Information (PHI) prior to obtaining HIPAA Authorization?

Yes

No

- *If yes, a "Partial Waiver of HIPAA Authorization" is required. Be sure to make this selection in the "HIPAA & Confidentiality" section below and complete [Addendum E: Waiver/Alteration of HIPAA Authorization](#)*

9.3 Recruitment of Potential Participants:

- All consecutive infants admitted during the study period at the NICUs of CMKC or KUMC who meet eligibility criteria for the study will be automatically included in the study.

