12.0 Follow-up

- All study infants will be followed throughout their course in the NICU, from admission to discharge. All data will be collected through clinical chart review. Follow-up will end once infants are discharged from the NICU. We will collect the following data points: (1) baseline characteristics (gestational age, birth weight, sex, race, mode of delivery, Apgar scores; (2) clinical characteristics at time of NEC concern (clinical presentation, age at time of NEC concern, results of diagnostic tests for NEC concern, information on treatment including days to full enteral feeds and days on antibiotics); and clinical outcomes at discharge (total length of stay, age at discharge, co-morbidities during NICU admission).

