25.0 Withdrawal of Participants*

25.1 A subject may be withdrawn from participation if they were transferred to another outside hospital or if they undergo exploratory laparotomy with ostomy and mucus fistula creation during the course of their admission as this procedure can preclude them from safely undergoing a BUS.

25.2 Subjects may also be discontinued from the study at the discretion of the site investigator as deemed appropriate for any reason.

25.3 If a subject withdraws from the research study, data that has already been collected may still be used; however, no new information will be collected except information related to adverse events or other safety issues.

DATA MANAGEMENT

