28.0 Statistical Analysis*

28.1 We will use two-tailed McNemar's test with paired measures to analyze differences in diagnostic thinking efficacy and therapeutic efficacy from pre- and post-BUS surveys. Comparison of duration of antibiotics, bowel rest, and days to full enteral feeds will be performed using Student's t-test. Kaplan-Meier curve will be used to analyze time to full feeds between the 2 groups, censoring for death, discharge/transfer out of the hospital, or 30 days following initial NEC concern. Analyses of patient outcomes (duration of bowel rest, duration of antibiotics, time to full feeds) will follow the intention-to-treat principle, with statistical significance set at a P value of < 0.05.

28.2 We will use t-test to analyze differences in mean time of BUS image acquisition and reporting. Chi-square test will be used to compare differences in proportion of BUS studies that were performed and reported per standardized protocol. Inter-rater reliability for BUS studies will be assessed by Cohen's kappa statistics.

28.3 Sample size was calculated based on our pilot study which demonstrated a mean \pm SD of duration to full enteral feeds of 16 ± 9 days per episode of NEC concern. Using this information, we generated Table 1, which shows sample sizes for a range of possible means and standard deviations, with significance level of 0.05 and 80% power. For a 1-year study with 67 to 81 distinct episodes, for an SD of +8 days, we anticipate having sufficient sample size to detect a 5- to 6-day difference in mean duration to full feeds (highlighted in gray in Table 1).

Difference of means between groups	Expected Standard Deviation		
	± 8	± 9	± 10
4 days	126	160	198
5 days	81	102	126
6 days	56	72	88

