32.0 Setting & Locations*

32.1 The NICU at CMKC is an 87-bed level IV NICU. Majority of infants admitted at the NICU are born at other hospitals and are typically transferred to CMKC due to need for specialized care. Neonatologists are in-house 24/7. As a children's hospital, radiology staff at CMKC are composed of pediatric sonographers and pediatric radiologists. BUS for NEC evaluation has been available at CMKC since 2015. Despite its availability, current use of BUS for NEC evaluation at CMKC remains highly variable, often dependent upon the individual preferences of the treating neonatologist.

32.2 The NICU at KUMC is a 32-bed level III NICU. Majority of infants admitted at the NICU are born at KUMC. Neonatology coverage at KUMC is provided by CMKC neonatologists who are also in-house 24/7. As a general adult hospital, radiology staff at KUMC are composed primarily of adult sonographers and adult radiologists. Currently, only one radiologist at KUMC has the expertise to perform BUS for NEC evaluation. Because of this limited availability, BUS for NEC evaluation is infrequently performed at KUMC. However, as part of our study's aim of investigating

generalizability of BUS in NICUs of adult hospitals, pre-study training will be done to standardize performance and availability of BUS between CMKC and KUMC.

32.3 Close research collaboration exists between the NICUs of CMKC and KUMC. Several research protocols done at CMKC are also done at KUMC. In fact, KUMC is such an active site for collaborative research that a CMKC-employed neonatology research coordinator ([name]) is dedicated solely for recruitment of participants at KUMC-NICU. Although KUMC has its own IRB, majority of the research done at KUMC NICU is approved via reliance on the IRB at CMKC.

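### Time to full feeds is censored at transfer out of the hospital with no exception for transfer between the two study NICUs, where the outcome could still be read from the chart

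*Combined protocol and SAP*

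**What the plan says.** Four rules in the combined protocol and SAP meet when an infant moves between the study NICUs.

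- **Censoring (28.1).** The Kaplan-Meier analysis of time to full feeds is specified as "censoring for death, discharge/transfer out of the hospital, or 30 days following initial NEC concern". The same section commits the patient-outcome analyses to intention-to-treat.
- **Withdrawal (25.1, 25.3).** "A subject may be withdrawn from participation if they were transferred to another outside hospital". After withdrawal, "no new information will be collected except information related to adverse events or other safety issues".
- **End of follow-up (12.0).** "Follow-up will end once infants are discharged from the NICU". The section does not say whether this means the first NICU or the last study NICU.
- **Entry (9.3).** "All consecutive infants admitted during the study period at the NICUs of CMKC or KUMC" are included automatically if eligible. Nothing is said about an infant already enrolled at the other site.

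On the setting, 32.1 says of CMKC: "Majority of infants admitted at the NICU are born at other hospitals and are typically transferred to CMKC due to need for specialized care". Section 32.2 describes KUMC as a level III NICU with mostly inborn infants, covered by CMKC neonatologists. Addendum B, in its argument on selection bias, says CMKC draws referrals from all of Kansas and western Missouri.

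**The concern.** Kaplan-Meier assumes that a censored infant has the same outlook as those still under observation. An infant moved from a level III to a level IV NICU because suspected NEC is worsening probably does not: full feeds are likely to come late. Censoring at that move makes feeding recovery look faster than it was.

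For most transfers this is hard to avoid, because the receiving hospital is outside the study. Here the receiving hospital may be the other study site, with the same protocol, the same IRB of record and outcomes taken from chart review. Censoring there discards an outcome that the team can reach, which fits poorly with the intention-to-treat commitment in 28.1. The infants affected would come from the less specialised setting that Aim 1 sets out to inform.

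The gap also reaches the count of infants. No visible rule says that an infant already enrolled at one site stays a single record when admitted to the other.

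**Working it through.** **1. The plan's own figure.** Table 1 (28.3) gives 81 for a 5-day difference, SD 8, alpha 0.05 and 80% power. Total N = 4 × [SD × (z₀.₉₇₅ + z₀.₈₀) / difference]² = 4 × [8 × (1.960 + 0.842) / 5]² = 80.4, so 81. The other eight cells also reproduce within rounding. The sample size is not in dispute.

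**2. Inputs.**
- KUMC share: 80 of 200 neonates (8.0) = 40%.
- Days to full feeds: mean 16, SD 9 (pilot, 28.3).
- Assumed, because the documents give no value: a share f = 5%, 10% or 20% of KUMC infants is transferred. As a worst case these are the slowest feeders at KUMC, and all are censored on day 3.
- Assumed: a gamma distribution with the pilot mean and SD (shape (16/9)² = 3.16, scale 81/16 = 5.06), the same at both sites.

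**3. Effect on the pooled Kaplan-Meier median.** The censored share of all infants is c = 0.4 × f. After day 3 the Kaplan-Meier curve is S(3) × [S(t) − c] / [S(3) − c], where S is the true curve. For this gamma, S(3) = 0.983. Setting the expression to 0.5 means reading the true curve at S(t) = c + 0.5 × [S(3) − c] / S(3).

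| f | c | S(t) at the apparent median | Apparent median (days) | Shift from 14.3 (days) |
|---|---|---|---|---|
| 5% | 0.02 | 0.510 | 14.1 | 0.2 |
| 10% | 0.04 | 0.520 | 13.9 | 0.4 |
| 20% | 0.08 | 0.539 | 13.5 | 0.8 |

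A simulation of 400,000 infants gives the same medians.

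**4. Effect on the mean, if the t-test drops these infants.** The censoring clause belongs to the Kaplan-Meier analysis, and 28.1 does not say how the t-tests treat a transferred infant. If they are left out under the same worst case, the mean falls from 16.0 to 15.5, 15.2 or 14.8 days.

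**5. Effect on power, if they are lost altogether.** Remaining N = 81 × (1 − c) = 79.4, 77.8 or 74.5. With power = Φ(5 / (8 × √(4/N)) − 1.96), 80.3% becomes 79.5%, 78.7% or 77.0%.

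**6. Shift in level or bias between arms.** The shifts in steps 3 and 4 apply equally to both arms if transfer is unrelated to arm. As an outer limit within these assumptions, suppose one arm loses the slowest 20% of its KUMC infants and the other loses none. The spurious difference is then 14.3 − 13.5 = 0.8 days in medians, or 16.0 − 14.8 = 1.2 days in means. The planned difference in means is 5 to 6 days.

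**7. Number of infants involved.** 5% to 20% of 80 KUMC infants is 4 to 16. At a total of 81, KUMC supplies 0.4 × 81 = 32.4, and the same rates give 1.6 to 6.5.

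**The case against.** The strongest reply is that the problem transfer is undocumented. Section 32.1 says CMKC takes infants from other hospitals but does not name KUMC as a source, and no rate or severity is given for moves out of KUMC. A reader might infer that KUMC's sickest infants are being cut off. The documents do not support that as fact, only as a foreseeable possibility given the two levels of care.

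Section 25.1 is permissive, and an outside hospital can fairly be read as one outside the study. That stands: 25.1 is ambiguous and does not clearly cover moves between the sites. The reading does not rescue 28.1, whose censoring clause refers to leaving the hospital and carries no such qualifier.

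A reader might also infer that a transferred infant re-enters at CMKC as a new subject, perhaps in the other arm. The text points the other way on the arm: 10.7 keeps infants in one arm throughout the study, birth month does not change on transfer, and date of birth and MRN are recorded. Separate calendars for the two NICUs would be needed for a switch, and the plan describes neither separate calendars nor a shared one. The detailed eligibility text is not in the supplied documents, so a bar on re-enrolment may exist there. What remains is that no linkage or single-record rule is visible.

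Finally, one might claim an overstatement of 5 to 20 percentage points in feeding success at KUMC. That would describe a KUMC-only curve, which the plan does not specify. The planned comparison is between arms.

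**Conclusion.** The point holds in a narrow form. The censoring rule in 28.1 has no exception for transfer between the two study NICUs, and 25.1 and 12.0 do not settle the matter. Applied literally, it discards an outcome that can be collected, and the loss is informative if such moves are for escalation of care.

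The size is modest: a shift of about 0.2 to 0.8 days in the pooled median and at most about 3 percentage points of power (80.3% to 77.0%). These figures rest on the assumed 5% to 20% transfer rate, the gamma shape and a deliberately unfavourable choice of infants and censoring day. They show a change in level. A biased treatment effect would need transfer, or the prognosis of those transferred, to differ by arm. There is a conceivable route, since BUS results go to the care team (10.3) and Aim 1 expects BUS to change the therapy plan, but the documents contain no data on it.

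Double entry is possible and not established. The change is worth making because it is cheap and retains data, not because the trial's conclusion is shown to be at risk.

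**What to change.** - **28.1:** replace the transfer part of the censoring clause with *transfer to a hospital other than CMKC or KUMC*. Say also how the t-tests treat infants transferred to a non-study hospital before full feeds.
- **25.1:** define an outside hospital as one that is neither CMKC nor KUMC.
- **12.0:** state that, for an infant moved between the study NICUs, follow-up continues until discharge from the receiving study NICU.
- **9.3 or 10.7:** state that such an infant keeps one study ID, the original arm and the original site for analysis, and is not enrolled again. Outcome dates are collected at the receiving study NICU.

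The cost is protocol and SAP wording plus linking a few records across two hospitals. Both sites work under one protocol, KUMC relies on the CMKC IRB (33.0), outcome data come from chart review (12.0), and a research coordinator is already dedicated to KUMC (32.3). If moves between the sites prove rare, little effort is spent.

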Specific aim #2: To determine the capability of implementing BUS for NEC evaluation in a level III NICU within an adult hospital. We hypothesize that BUS timeliness, quality, and inter-rater reliability are comparable between level III and IV NICUs.

The addition of BUS to the diagnostic repertoire of infants with suspected NEC is an important contribution to neonatology. Before widespread adoption can be realized, however, strong evidence is needed to determine whether the addition of BUS would lead to actual clinical benefits, including in level III NICUs in adult hospitals. We anticipate that our study will help address this critical gap in knowledge and provide important insights as to the safe and effective use of BUS for NEC.

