10.6 Follow-up imaging

Infants with suspected NEC may need additional follow-up imaging for ongoing concerns of NEC. If the treating neonatologist deems follow-up imaging is needed, study infants will continue to have either AXR or AXR + BUS performed as determined by their randomization arm.

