10.7 Multiple episodes of NEC concern

Infants may also develop more than one episode of NEC concern during their admission. For such instances, study infants will remain in the same randomization arm throughout the study.

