26.0 Data Collection*

26.1 The study will collect baseline clinical characteristics, lab test results, AXR and BUS results, clinical diagnosis, treatment data, and survey results.

- Clinical characteristics: gestational age at birth, weight at birth, sex, race/ethnicity, age at time of NEC concern,
- Lab test results: complete blood cell count (CBC), C-reactive protein (CRP), blood culture
- AXR and BUS results: time of order input in the chart, time of image acquisition, time of reporting, text of report and interpretation by radiologist
- Clinical diagnosis: NEC, no NEC, food protein-induced enterocolitis, clinical sepsis, other diagnosis

- Treatment data: medical treatment of NEC including days of bowel rest, days to full enteral feeds, days on antibiotics; surgical treatment of NEC including peritoneal drainage or exploratory laparotomy
- Survey results: post-AXR survey and post-BUS survey by neonatologists

26.2 Data will be obtained from the electronic medical record and surveys/questionnaires.

26.3 Sensitive Data: We will not be collecting or accessing sensitive data.

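### Section 28.2 compares BUS exams between sites without limiting Aim 2 to one exam per infant or allowing for repeats, so p-values and intervals would be too optimistic

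*Combined protocol and SAP*

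**What the plan says.** Section 1.0 gives the Aim 2 hypothesis: "We hypothesize that BUS timeliness, quality, and inter-rater reliability are comparable between level III and IV NICUs". Section 28.2 supplies three methods for it:

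- Timeliness: "We will use t-test to analyze differences in mean time of BUS image acquisition and reporting". No unit of analysis is named.
- Quality: "Chi-square test will be used to compare differences in proportion of BUS studies that were performed and reported per standardized protocol". The unit is the BUS study.
- Reliability: "Inter-rater reliability for BUS studies will be assessed by Cohen's kappa statistics". The unit is again the BUS study. No test or interval for kappa is specified.

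Two other sections mean that one infant can contribute several BUS. On follow-up within an episode, section 10.6 says: "If the treating neonatologist deems follow-up imaging is needed, study infants will continue to have either AXR or AXR + BUS performed", according to arm. On further episodes, section 10.7 says: "For such instances, study infants will remain in the same randomization arm throughout the study".

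For each imaging result, section 26.1 records "time of order input in the chart, time of image acquisition, time of reporting, text of report and interpretation by radiologist". Section 24.2 adds exam dates and the record number. The plan does not limit Aim 2 to one exam per infant, separate first from follow-up exams, or name a method for repeated exams. It gives no sample size, power or expected number of BUS for Aim 2.

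**The concern.** The t-test and the chi-square test assume independent observations. Exams of one infant share that infant's condition and may share staff, so they are likely to be correlated. If every exam is entered as a separate observation, the standard error of the site difference is too small. False site differences then appear more often than 5% of the time, and any interval used to support comparability is too narrow.

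A second mechanism is separate from the first. A first BUS is part of an urgent work-up (Addendum B describes stat evaluation), whereas a follow-up BUS may differ in timing or in conformance to the standardized protocol. If it does, and if the sites differ in the share of exams that are follow-ups, a pooled comparison partly measures that share. More data do not remove this bias.

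Aim 2 is one of two specific aims. Leaving the unit open also allows it to be chosen after the data are seen.

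**Working it through.** **The plan's own figure.** The only sample-size figures are in Table 1 of section 28.3 and concern Aim 1. For a 5-day difference and SD 8, total N = 4 × (8 × (1.960 + 0.842) / 5)² = 80.4. The table gives 81; two equal groups of whole infants need 82. The other eight cells reproduce exactly. None of this bears on Aim 2, so there is no Aim 2 figure to reproduce.

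**Inputs.**

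- Infants: 120 at CMKC and 80 at KUMC (section 8.0). With an even split by arm (assumption), about 60 and 40 have BUS. Addendum B also mentions a target of 80 infants. Split 1:1 by arm and 60:40 by site (assumption), that gives about 24 and 16.
- Significance level: 0.05 is stated for patient outcomes only. Two-sided 0.05 is assumed for Aim 2.
- Exams per infant (m), ICC, conformance rate and exam times: none is given in the documents. All are assumed below.

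**Clustering, equal numbers of exams.** Design effect DE = 1 + (m − 1) × ICC. Actual error = 2 × (1 − Φ(1.96 / √DE)). A naive interval has 1/√DE of its proper width.

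| m | ICC | DE | Actual error | Interval width vs proper |
|---|---|---|---|---|
| 1.5 | 0.1 | 1.05 | 5.6% | 0.98 |
| 2 | 0.1 | 1.1 | 6.2% | 0.95 |
| 3 | 0.3 | 1.6 | 12.1% | 0.79 |
| 4 | 0.5 | 2.5 | 21.5% | 0.63 |

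**Clustering, simulated with unequal numbers.** There was no true site difference, exams per infant were 1 + Poisson, and conformance was 80%. Each setting had 4000 runs. Rejection rates for chi-square / t-test with 60 + 40 infants:

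| Mean exams | ICC 0.1 | ICC 0.3 | ICC 0.5 |
|---|---|---|---|
| 1 | 5.1 / 5.2% | 5.1 / 4.6% | 4.8 / 4.5% |
| 2 | 6.8 / 6.6% | 10.9 / 10.1% | 13.4 / 14.4% |
| 3 | 8.2 / 8.5% | 13.9 / 14.2% | 20.9 / 19.5% |
| 4 | 9.7 / 9.8% | 17.3 / 17.9% | 24.4 / 25.2% |

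With 24 + 16 infants and 2 to 4 exams, the range is 7.0% to 25.3%. With one exam per infant, the rates across both cases are 4.3% to 5.2%.

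The simulated rates exceed the equal-size formula because infants with many exams weigh more: DE = 1 + (E[m²]/E[m] − 1) × ICC. For mean 4, E[m²] = 16 + 3 = 19 and 19/4 = 4.75, so at ICC 0.5 DE = 1 + 3.75 × 0.5 = 2.875. The actual error is then about 25%, in line with the table.

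**Mix of first and follow-up exams (illustration, all inputs assumed).**

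- Timeliness: a first BUS takes 2 h and a follow-up 8 h at both sites. With one follow-up per infant the site mean is (2 + 8)/2 = 5.0 h; with two it is (2 + 16)/3 = 6.0 h. Service is identical, yet the gap is 1 h.
- Quality, false gap: conformance is 70% for first and 90% for follow-up exams at both sites. A follow-up share of 67% gives 0.33 × 70 + 0.67 × 90 = 83.4%. A share of 33% gives 0.67 × 70 + 0.33 × 90 = 76.6%. The gap is 6.8 points.
- Quality, hidden gap: one site is 10 points worse for both exam types (60% and 80%) and has a follow-up share of 75%, so it scores 0.25 × 60 + 0.75 × 80 = 75.0%. The other site (70% and 90%) scores 76.6% at a share of 33% and 75.0% at 25%. The true 10 points shrink to 1.6 or to 0.

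**The case against.** The strongest reply is that the plan is silent here, not wrong, and that the size of any harm is unknown. Much of that stands.

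- A reader might infer that the plan expressly pools all exams and uses the exam as the unit for all three methods. It does neither. It never says outright that follow-up exams enter Aim 2, and it names no unit for the t-test. What remains is that the quality test is defined on BUS studies with no restriction, so following the text literally pools repeats as independent.
- A reader might infer that kappa is invalidated. Repeats do not invalidate the estimate itself; they affect its standard error, and section 28.2 plans no interval or test for kappa.
- The ICC may be low. Order-to-image time could depend mainly on sonographer availability and little on the infant. With few repeats the inflation is then slight, hence the 5.6% at the bottom of the range.
- Inflated type I error produces false differences, which works against the hypothesis of comparability. This is true, but intervals that are too narrow also overstate how firmly comparability has been shown.
- A reader might infer that CMKC, as the referral unit, will order more follow-up BUS and so bias the comparison. The documents give no follow-up counts. CMKC neonatologists cover both units (section 32.2), and the treating neonatologist decides on follow-up (section 10.6). Withdrawal after laparotomy with ostomy and mucus fistula (section 25.1) may cut short repeats in some of the sickest infants. KUMC is itself a referral centre for high-risk pregnancies (Addendum B). The mix effect is therefore a possibility only.
- Follow-up imaging for continuing concern is also NEC evaluation, so first-exam-only is one sound choice among several. A clustered analysis of all exams is another.

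**Conclusion.** The point holds in limited form. Section 28.2 leaves the Aim 2 unit undefined for times and sets it at the BUS study for quality, while sections 10.6 and 10.7 generate repeat exams that no method in the plan accounts for. Analysed as written, site comparisons would be anti-conservative. The inflation runs from negligible to a several-fold excess over 5%, depending on exams per infant and ICC, and the documents do not let one say where in that range the trial will fall. Bias from an unequal first/follow-up mix is conditional on two undocumented differences and is not an established defect. The issue should be settled before analysis because it affects one of the trial's two aims and is cheap to correct. It does not touch the Aim 1 comparisons.

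**What to change.** Amend section 28.2 as follows.

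1. State that the main Aim 2 comparisons of timeliness and quality use the first BUS of each infant's first episode, so that each infant contributes one exam.
2. As a supporting analysis, use all BUS with standard errors clustered on infant (GEE or a bootstrap by infant) and first/follow-up as a covariate.
3. If a kappa interval is reported with repeats included, bootstrap by infant.

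No new data field is needed, because exam order can be derived from the exam dates (section 24.2) and the order and acquisition times (section 26.1).

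The cost is SAP wording plus fewer exams in the main comparison: on the assumptions above, about 60 versus 40, or 24 versus 16. The loss of information is smaller than the loss in count, since correlated repeats add less than their number suggests, and the supporting analysis still uses them.

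### Aim 2 has no measure of whether infants assigned to AXR + BUS received a BUS, so the sites can look comparable when one delivers it less often

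*Combined protocol and SAP*

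**What the plan says.** The aim in section 1.0 is "To determine the capability of implementing BUS for NEC evaluation in a level III NICU within an adult hospital". Its hypothesis reads: "We hypothesize that BUS timeliness, quality, and inter-rater reliability are comparable between level III and IV NICUs".

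Section 28.2 gives three analyses for it:
- Timeliness: "We will use t-test to analyze differences in mean time of BUS image acquisition and reporting".
- Quality: a chi-square test to "compare differences in proportion of BUS studies that were performed and reported per standardized protocol".
- Reliability: Cohen's kappa, on BUS studies.

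The intention-to-treat statement in section 28.1 names bowel rest, antibiotics and time to full feeds only. It does not reach Aim 2.

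On delivery, section 10.3 provides that every infant in the AXR + BUS arm has both tests ordered and performed. Section 10.5 deals with AXR-arm infants who get a BUS, but nothing deals with AXR + BUS infants who do not. Section 32.2 states: "Currently, only one radiologist at KUMC has the expertise to perform BUS for NEC evaluation". It gives this limited availability as the reason BUS is infrequent there, and adds that training before the study is meant to bring the two sites level in both performance and availability.

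Section 26.1 collects, for AXR and BUS, "time of order input in the chart, time of image acquisition, time of reporting".

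**The concern.** The plainest way for a site to fall short on implementation is that a BUS called for by the randomization calendar does not happen. None of the three measures is built to record this. An undone BUS has no acquisition time, so the t-test omits it on any reading. For the chi-square test the denominator is unclear. If it is studies done, every undone BUS is lost. If it is studies ordered, an order left unfilled counts as a failure, but an infant for whom no order was entered is still lost.

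Availability is the difficulty that the protocol itself names at KUMC, and Addendum B notes that NEC concern can arise at any hour. The planned training is aimed at that difficulty, yet no endpoint checks whether it worked. Aim 2 could therefore report comparable timeliness and quality while the share of assigned infants who received a BUS differs between sites and goes unreported.

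**Working it through.** **Plan's own figure.** There is none to reproduce. No sample size, margin, power or delivery rate is stated for Aim 2; Table 1 in section 28.3 concerns time to full feeds.

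**Inputs.**
- Enrolment goals: CMKC 120 and KUMC 80 infants (section 8.0).
- Assumed: equal arms, so 120/2 = 60 and 80/2 = 40 infants assigned to AXR + BUS.
- Assumed: 90% adherence to the standardized protocol among studies done, at both sites.
- Assumed: 100% delivery at CMKC, and 90% down to 50% at KUMC.

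**Adherence.** At CMKC, 0.90 × 60 = 54 successes. At KUMC, studies done = 40 × delivery rate, and successes = 0.90 × studies done, rounded to whole infants. P is from the Pearson chi-square test without continuity correction. Power is the normal approximation for two proportions on the unrounded rates, two-sided 0.05.

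| KUMC delivery | Done-only, CMKC v KUMC | P | All assigned, CMKC v KUMC | P | Power, all assigned |
|---|---|---|---|---|---|
| 90% | 54/60 = 90% v 32/36 = 89% | 0.86 | 90% v 32/40 = 80% | 0.16 | 26% |
| 80% | 90% v 29/32 = 91% | 0.92 | 90% v 29/40 = 72.5% | 0.022 | 64% |
| 70% | 90% v 25/28 = 89% | 0.92 | 90% v 25/40 = 62.5% | 0.0009 | 90% |
| 50% | 90% v 18/20 = 90% | 1.0 | 90% v 18/40 = 45% | < 0.0001 | > 99% |

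Example, 80% row: pooled proportion (54 + 29)/100 = 0.83; z = (0.900 − 0.725)/√(0.83 × 0.17 × (1/60 + 1/40)) = 0.175/0.0767 = 2.28; P = 0.022.

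**Sensitivity.**
- If CMKC delivers 95%, power at KUMC delivery of 90%, 80%, 70% and 50% falls to 9%, 39%, 73% and 99%.
- Addendum B works from a target of 80 infants. With 40 in the AXR + BUS arm, split 60:40 by site as in section 8.0 (24 v 16), and full CMKC delivery, power is 14%, 32%, 54% and 88%.

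**Timeliness.** A simulation of 4,000 runs per setting assumed the same time distribution at both sites (gamma, mean 4 h, SD 2 h), 60 v 40 assigned, and non-delivery at KUMC unrelated to time. At KUMC delivery of 100%, 80%, 60% and 50%:
- The t-test on studies done rejected in 5.0%, 4.4%, 4.9% and 5.3% of runs, about its nominal error rate throughout.
- A comparison over all assigned infants (BUS acquired within an assumed 6 h, undone counted as not achieved) rejected in 4.7%, 53%, 96% and 99.7%.

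**The case against.** Several points on the other side have weight.

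1. A reader might infer that infants without a BUS certainly drop out of the adherence proportion. The wording does not settle that. Performance can be read as part of what is being counted, so that an ordered but undone study is a failure. This stands for the chi-square test as far as orders go. It does not help where no BUS was ordered, and it does not help the t-test.

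2. The hypothesis speaks of timeliness, quality and reliability, which are properties of completed studies. That is so, but the aim it serves is the capability to implement BUS, and delivery is part of that.

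3. The plan acts against non-delivery: training, an arm calendar posted in the workroom (section 10.2), and bi-weekly team review (section 27.1). The single expert radiologist describes the position before training. These steps may reduce non-delivery; they do not measure it. Nothing in the documents shows that KUMC will in fact under-deliver.

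4. Shortage of capacity may appear as delay or off-protocol studies, which the planned tests would see. Only non-delivery escapes them.

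5. Section 10.6 says that "study infants will continue to have either AXR or AXR + BUS performed as determined by their randomization arm", and section 10.5 allows cross-over, so a reader might infer that follow-up and cross-over BUS are pooled with the first urgent one. The documents do not say so, and cross-over is expected to be rare. Section 28.2 simply does not state which BUS is analysed.

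6. Counting every undone BUS as a site failure would be too harsh. Section 25.1 allows withdrawal for transfer or after laparotomy with ostomy, which is not lack of availability. A clock started at the AXR order also mixes the clinician's ordering delay with radiology performance. Both points are accepted in the proposed change.

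**Conclusion.** The concern holds in a limited form. Section 28.2 contains no measure of BUS delivery among assigned infants. The time comparison is confined to BUS that took place, and the adherence denominator is ambiguous and misses unordered BUS on either reading. The sites can therefore look comparable when one delivers BUS less often.

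How much this matters cannot be fixed from the documents, because they give no delivery rate. Under the stated assumptions the hidden gap in adherence is 10 percentage points at 90% KUMC delivery, 17.5 at 80% and 45 at 50%. Near 90% the distortion is modest, and the all-assigned test would usually be non-significant as well (power 26%, or 14% at the smaller target), so the proportions themselves matter more there than the P value. The point concerns Aim 2 only; the Aim 1 patient outcomes are under intention-to-treat.

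**What to change.** In section 28.2:

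1. Take as denominator, by site, all infants assigned to AXR + BUS by birth month, at their first NEC concern. Report the proportion with a BUS performed, and the proportion with a BUS performed and reported per protocol. Not ordered or not done counts as not achieved.
2. Tabulate the reasons for each undone BUS. Show infants withdrawn for transfer or laparotomy with ostomy (section 25.1) separately from lack of availability.
3. Analyse time to BUS acquisition and to report over all assigned infants, from a start that each of them has: the AXR order of that episode. Keep an undone BUS in the analysis as not achieved. Retain BUS order-to-acquisition time among studies done as a secondary measure, since it isolates radiology performance.
4. State that these comparisons use the first BUS of the first episode in the AXR + BUS arm.

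The times are already collected under section 26.1, and the arm follows from birth month (section 10.2), so infants with no BUS order can be identified. Beyond recording reasons, the cost is redefined Aim 2 endpoints and a little more analysis. The delivery figures may look less favourable.
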